### **Subject Withdrawal or Termination**

Subjects are free to withdraw from the study at any time and will be withdrawn if they inform Tandem that they no longer wish to participate. Data collected prior to the subject's withdrawal will remain part of the study record and will be included in the analyses. All participants that have been successfully enrolled in the study will receive regular invitations to provide data. A Retention Management protocol will be initiated to attempt to re-engage participants that do not respond after three separate outreach attempts.

## **TREATMENT OF SUBJECTS**

### **The t:slim X2 insulin pump with Control-IQ technology**

The Control-IQ System is a US FDA-approved device indicated for the treatment of type 1 diabetes in people age 6 years and older. The Control-IQ System is integrated with the Dexcom G6 CGM and uses CGM values to adjust insulin delivery with the goal of improving glucose control (time in range of 70-180 mg/dL).

#### **Initiation of therapy with the Control-IQ System:**

- Subjects will be recruited from the population of patients initiating therapy with Control-IQ after it has been prescribed by a licensed healthcare professional.
- Subjects new to the Tandem X2 insulin pump will receive a new pump with Control-IQ technology
  - These subjects might be new to insulin pump therapy or might be switching from a different brand or type of insulin pump.
- Subjects who own a t:slim X2 insulin pump will receive a remote software update and download the Control-IQ technology onto their existing t:slim X2 insulin pump.

#### **Enrollment procedure:**

The enrollment process has been detailed in the flowchart in **APPENDIX A**. Study subjects will be enrolled using customer recruitment filters and triggers from two data sources housed within Tandem – (a) the CRM (or the Custom Relationship Management Technology) and (b) the t:connect® customer portal (web secure application designed for Tandem users to request prescriptions for any pump-related updates and complete necessary trainings). Daily automatic recruitment invite contact lists, defined by study inclusion and exclusion criteria, will be generated for eligible Tandem users and using a

secure file transfer protocol, and Qualtrics (a HIPPA compliant survey and report generating software) will deploy automated survey invites daily (via email or SMS text). The first study invite will include important information about the study eligibility criteria and an invitation to start the informed consent process, including a Release of Medical Records form and the baseline questionnaires (baseline adverse events and other PRO measures). Tandem users who indicate that they are not interested in participating will be removed from the potential recruitment list and will not receive any further communication about the study. The remaining users will receive reminder emails (as needed) and those interested will complete the IRB approved electronic consent form by providing their digital signature.

**Duration of therapy and follow-up:** All enrolled subjects who initiate therapy with the Control-IQ System will be monitored from baseline through 12 months following the initiation of treatment. Participants will be considered screen failures if Control-IQ data has not been downloaded to t:connect 120 days after the baseline survey's completion.

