**Table 1: Protocol Revision History**

Draft Number	Amendment Approval Date	Brief Description of Changes
01	N/A	Initial Draft Version
02	April 30, 2020	Included literature review and evaluable study endpoints; added severe hypoglycemia and DKA education to participant messaging; adjusted criteria for withdrawal from study; added options for obtaining information on inclusion/exclusion criteria and AEs; clarified CGM-autopopulated bolus analysis; and clarified definition of “CGM-naïve”
03		Changed name to Control-IQ Observational (CLIO) Post-approval Study. Amended inclusion/exclusion criteria and enrollment targets to include subjects ages 6 years and older.
04	August 19, 2020	In response to FDA request, adjusted enrollment targets for subjects ages 6-13 years old.
05	October 22, 2020	Revised wording to provide clarity to the original intention of the target enrollment sample size for the study, which was to recruit a minimum of 2063 subjects.
06.1	June 28, 2021	
Changed inclusion criteria to “Agree to provide HbA1c result, obtained within the 6-month period prior to enrollment”.
 
Added to Medical History: Participants already recruited during the COVID emergency who did not have a recent HbA1c result within the past 6 months of enrollment will not be counted toward overall recruitment goals, and will be analyzed separately.
 
Participants will be considered screen failures if Control-IQ data has not been downloaded to t:connect 120 days after the baseline survey’s completion. Currently ~24% of CLIO participants that have completed their initial baseline questionnaire have not progressed to the Month 1 Survey. To avoid prolonging the overall duration of the CLIO study the individuals will be considered screen failures if they have not downloaded Control-IQ data to t:connect within

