		
120 days. The period of 120 days was chosen because on average 98% of CLIO's currently active participants initiated therapy with Control-IQ within that timeframe.
 
Corrected text throughout document that mentioned that Medical Release Forms would be collected for all participants during the informed consent process. Medical Release Forms are only being collected from participants if they report adverse events that require additional information for reporting purposes.
 
Included that participants will be contacted regarding reported adverse events to the Adverse Events section.
 
Added that as part of the enrollment process as specific target subgroups are filled, we may elect to only enroll subjects whose subgroup recruitment goals have not been completed.
 
Change PI to [name]

07	February 17, 2022	
Clarified throughout document which information would be directly entered into the EDC (i.e. participant survey responses) versus verified and entered into eCRF by trained study personnel (i.e. adverse event information).
 
Additional background material added on CGM naïve children who started Control-IQ technology, with a new reference to: (10) Renard E, Tubiana-Rufi N, Bonnemaison E, Coutant R, Della-Vale F, Bismuth E, et al. Outcomes of Hybrid Closed-Loop Insulin Delivery Activated 24/7 versus Evening and Night in Free-living Pre-pubertal Children with Type 1 Diabetes. A Multicenter Randomized Clinical Trial. Diabetes Obes Metab. epub ahead of print, November 23, 2021.
 
Removed text, "Recruitment of CGM-naïve children in our previous clinical trial did not achieve the pre-specified target of 20%", and added per the recent data published in CGM naïve participants in (10) where 33% of

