### **Study Endpoints**

- Primary Safety Endpoints: Composite rate of severe hypoglycemia and diabetic ketoacidosis through 12 months following initiation of therapy with the Control-IQ System.
- Secondary Effectiveness Endpoints
  - Glycemic outcomes (based on data from CGM sensor values):
    - % time in range (70-180 mg/dL)
    - % time <54 mg dL
    - % time <70 mg/dL
    - % time >180 mg/dL

- %time >250 mg/dL
- Patient-reported outcomes:
  - Satisfaction with device
  - Trust in the system
  - Usability of the system
  - Sleep quality

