## SUBJECT SELECTION

### Subject Population

**Inclusion Criteria:** Patients must consent to meet the following criteria in order to be enrolled in the study:

- 1) Patients with self-reported type 1 diabetes who have been prescribed the Control-IQ system.
- 2) At least 6 years of age
- 3) Using Humalog or Novolog insulin
- 4) For females, not pregnant or planning pregnancy in the next 12 months.
- 5) Agreement to use the t:slim X2 with Control-IQ technology, and to continue use for at least 12 consecutive months after study enrollment.
- 6) Agree to provide HbA1c result, obtained within the 6-month period prior to enrollment.
- 7) Ability to respond to alerts and alarms, and to provide basic diabetes self-management.
- 8) Patients who reside full-time in the United States.
- 9) Willingness to download the t:connect Mobile application to their Smartphone and keep it active throughout the study. Patients unable to use t:connect mobile application must be willing to manually upload their insulin pump data to t:connect every three months and at the completion of the study.
- 10) Subject has read, understood and agreed to participate in the study, and has electronically signed the Informed Consent Form (ICF).

**Exclusion Criteria:** Patients with the following characteristics will not be considered candidates for the study:

- 1) Self-reported type 2 diabetes
- 2) < 6 years of age
- 3) Use of any glucose-lowering therapy other than Humalog or Novolog insulin
- 4) Inability to respond to alerts and alarms, or to provide basic diabetes self-management.
- 5) Pregnancy
- 6) Subjects who have not signed the ICF.

Any discrepancy in the above criteria between data in CRM and subject's self-reported criteria will be electronically alerted to study staff. Study staff will then clarify inclusion/exclusion criteria prior to enrolling the subject.

Over the course of the study as specific participant recruitment subgroups are filled, we may enroll subjects whose subgroup goals have not been completed and elect to exclude otherwise applicable participants.

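### The day-120 screen-failure rule tests for uploaded data rather than for starting Control-IQ, so it can reclassify people who started, and nothing keeps their exposure and events in the primary safety rate

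*Combined protocol and SAP*

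**What the plan says.** **The rule.** Under Enrollment procedure, in the paragraph on duration of therapy and follow-up: "Participants will be considered screen failures if Control-IQ data has not been downloaded to t:connect 120 days after the baseline" survey's completion. The sentence just before it commits to something wider: "All enrolled subjects who initiate therapy with the Control-IQ System will be monitored from baseline through 12 months".

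**The endpoint.** Study Endpoints counts from the start of therapy and sets no upload condition: "Composite rate of severe hypoglycemia and diabetic ketoacidosis through 12 months following initiation of therapy with the Control-IQ System".

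**Permitted upload schedule.** Under inclusion criterion 9 (Subject Population), patients who cannot use the mobile app "must be willing to manually upload their insulin pump data to t:connect every three months". The text does not say when the three months begin.

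**Reason for 120 days.** The Protocol Revision History (amendment 06.1), used here only for the rationale, reports that on average 98% of "currently active participants initiated therapy with Control-IQ within that timeframe". It also notes: "Currently ~24% of CLIO participants that have completed their initial baseline questionnaire have not progressed to the Month 1 Survey".

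**Retention of data.** For subjects who withdraw, data collected beforehand "will remain part of the study record and will be included in the analyses". No matching sentence covers screen failures. No analysis set is defined, and Determination of Sample Size defers the detailed analysis plan.

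**The concern.** Starting therapy and uploading data are different events, and a participant can do the first without the second. A rule meant to remove people who never began is written so that it also catches people who began and did not upload.

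The label is applied up to 120 days after the baseline survey and depends on what the participant did in that time. In a study whose main purpose is to estimate the SH and DKA rates of users, that is selection on post-baseline behaviour. If starters without uploads have a different event rate from those retained, the primary rate no longer describes everyone exposed. If their rate is higher, the reported rate moves toward the success criterion of no higher incidence than the literature.

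Events in this group are at least partly observable without an upload. The synopsis has all support calls screened for SH and DKA, and the surveillance database is queried monthly (Observation and Recording of Adverse Events).

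**Working it through.** **Plan figures.** The 98% comes without counts and cannot be reproduced. The synopsis figure for completers can: 2,063 × 0.75 = 1,547.25, or 1,547.

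**Step 1. Which compliant manual uploaders are caught?** Take a quarter as about 91 days.

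| Upload clock runs from | First due upload containing Control-IQ data | Caught if start falls |
|---|---|---|
| Start of therapy (day s after the baseline survey) | s + 91 | s > 120 − 91 = 29, so after about day 29 |
| Baseline survey (uploads near days 91 and 182) | Day 91 if started by then, otherwise day 182 | Between about day 91 and day 120 |

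With a quarter of 90 to 92 days, the first threshold is day 30 to day 28. Under either clock some compliant participants are caught. Prompt starters who upload on time are not.

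**Step 2. How far could the rate move?** Let f be the share of all exposed person-time that is removed and r the event rate of those removed relative to those retained. Then

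retained rate ÷ all-exposed rate = 1 / (1 − f + f × r).

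Neither f nor r is in the documents, so the values below are assumptions. With r = 1 the ratio is 1 at any f. With r < 1 the rate is overstated.

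f is a share of person-time, not of people. A starter who leaves by day 120 contributes at most 120/365.25 = 0.3285 years. If 10% of starters do so and the other 90% contribute a full year:

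f = (0.10 × 0.3285) / (0.90 + 0.10 × 0.3285) = 0.03285 / 0.93285 = 3.5%.

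- At r = 2: 1 / 1.0352 = 0.966, an understatement of 3.4%. If the all-exposed rates equalled the benchmarks of 25.35 (SH) and 11.03 (DKA) per 100 patient years, the retained rates would be 24.49 and 10.65.
- If the same 10% would each have had a full year, f = 10%. At r = 2: 1 / 1.10 = 0.909, an understatement of 9.1%, with retained rates of 23.05 and 10.03.
- A milder case, 2% of starters leaving by day 120 with r = 1.5: f = 0.00657 / 0.98657 = 0.67%, an understatement of 0.3%.

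**Step 3. What would that do to the planned test?** Use the two-sided exact binomial test at 5%, N = 1,547 and r = 2. N is held fixed and each participant counts as one patient year. The true excesses (1.13 times benchmark for SH, 1.22 times for DKA) are chosen to be detectable with a little over 80% probability when nothing is removed.

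| Person-time removed (f) | Chance of flagging SH at 1.13 × | Chance of flagging DKA at 1.22 × |
|---|---|---|
| 0% | 83% | 83% |
| 2% | 67% | 74% |
| 5% | 40% | 58% |
| 10% | 9% | 31% |

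The 3.5% case lies between the second and third rows. These figures show sensitivity only; they are not estimates for this study.

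**The case against.** **The rule has a purpose.** The bolus-calculator endpoint and all glycemic endpoints need pump and CGM data, and in a fully remote study an upload is objective evidence of initiation. For people who never started, exclusion is correct. This stands, and the fix keeps upload as one form of evidence.

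**A reader might infer that the rule discards these people's events.** The text does not say so. It applies a label, while the adverse-event section promises documentation of all events in all subjects. What the documents support is narrower: the usual effect of the label is removal from analysis, and nothing prevents it. The enrollment flow chart (Appendix A) and adverse-event procedure (Appendix C) are not in the text available and may say more.

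**A reader might take the 24% as the size of the affected group.** It is not. It counts baseline completers who had not reached the Month 1 survey at one date, and may mix non-starters, non-uploaders and recent enrollees. The 98% does not help either, because it is conditioned on participants already active.

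**Monthly surveys may not reach non-uploaders.** The revision history answers slow progress to the Month 1 survey with an upload deadline, which suggests that survey follow-up may begin only once data arrive. If so, adding all their person-time would bring in exposure with incomplete event capture and could itself lower the rate. This stands and limits the fix.

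**The manual-upload group may be small.** It is open only to those unable to use the app, and only late starters within it are caught. Its size is not given.

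**Conclusion.** The point holds as a mismatch between trigger and purpose. The rule tests upload; its rationale, the adjacent follow-up commitment and the primary endpoint concern initiation. It can therefore label starters as screen failures, including compliant manual uploaders who start late, and no provision keeps their exposure and events.

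A reader might go further and conclude that the SH and DKA rates are biased downward by a known amount. The documents do not support that. Higher risk among non-uploaders is plausible but not shown, and nothing suggests it for compliant manual uploaders. Size and direction are undetermined: zero at equal risk, about 3.4% understatement under doubled risk with 10% of starters leaving by day 120, and about 9% only if those removed would have had full follow-up. The case for change rests on a safety population being selected on post-baseline behaviour with the effect unreported, not on any one of these figures.

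**What to change.** 1. Define screen failure as no evidence of initiation by day 120, where evidence is an upload, a self-reported start, or a support or surveillance contact showing use.
2. State when the three-month upload clock begins, and do not screen-fail a manual uploader before the first due upload.
3. Keep the SH and DKA events and person-time of everyone who started in the primary safety rate, limited to periods in which events were ascertained.
4. Report the number screen-failed by reason, and give a sensitivity rate including and excluding starters without uploads.

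Cost: a short amendment, plus a check of survey, support and surveillance records for evidence of start. The documents do not say whether activation is recorded elsewhere, so the definition should not depend on that. The downside is that some participants will have event data without pump or CGM data and will not contribute to the bolus-calculator and glycemic endpoints.

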## MEASUREMENTS AND EVALUATIONS

**Event Schedule:** The eCRFs will be completed by the investigator (or an authorized member of the investigator's staff) and entered into the EDC database per the event schedule described below.

**Baseline Data Collection:** The potential study subjects will be evaluated (initially via CRM filters) to ensure they are appropriate candidates for this post approval study. Interested subjects will be asked to sign the ICF electronically. Eligibility to enroll in the study will be assessed based on the inclusion/exclusion criteria and the fulfillment of specific target subgroup populations. The enrollment information will be entered via participant responses into the EDC system. In addition, demographic and relevant medical history will be collected at this time (see **APPENDIX A** for detailed steps in the screening and enrollment process).

**Subject Completion or Early Withdrawal:** The subject completes the study one year after initiating therapy with Control-IQ, or when they choose to withdraw from the study, if earlier than 1 year.

### Data Collection:

The data will be collected per the schedule outlined below:

Procedure/Assessment	Baseline*	Monthly	Months 3 and 6	Final
Informed Consent	X			
**Release of Medical Records				
Screening for eligibility	X			
Report of incoming AEs		X		X
Outreach for AEs	X	X		X
User Experience	X		X	X

Psychosocial Outcomes	X	X	X
-----------------------	---	---	---

\*Includes demographics, frequency of AEs

\*\*Only requested as needed to collect additional information on reported AEs

Investigators will be provided a process for assigning a de-identified number to the subject and will be required to keep any study paperwork or electronic files in a secure private area. Electronic audits will be in place to help ensure that data entered is within reasonable limits.

**Informed Consent Process:** All subjects must electronically sign the ICF (see **APPENDIX B**) approved by the IRB to be enrolled in the study. The subject will receive study team contact information (email and telephone) and be given ample opportunities to ask questions about the procedures, required schedule of data collection, and the benefits and risks of participating in the study before signing the ICF. All subjects will receive an electronic copy of the ICF to keep for their records. Subjects will be informed of any revisions to the ICF and any revisions must be electronically signed and kept in the subject study file. In addition, a signed Release of Medical Records form may be obtained if needed to collect additional information on reported Adverse Events to allow the investigators to obtain accurate event information when necessary. Acquisition of the informed consent, Release of Medical Records form (if applicable) and any revisions will be documented in the survey database.

**Demographics:** The following demographic data will be obtained: date of birth, gender, race, ethnicity, educational level, socioeconomic status, residence, employment status, weight, height, and type of health insurance.

**Medical History:** Medical history, including existing comorbidities deemed clinically relevant (e.g. retinopathy, nephropathy, neuropathy, history of cardiovascular events) will be collected at baseline. In addition, details specific to type 1 diabetes, including age at diagnosis, duration of disease, previous therapy, most recent HbA1c within the past 6 months, frequency of SH and DKA, and family history will be collected from the study subject in the baseline questionnaire.

Participants already recruited during the COVID emergency who did not have a recent HbA1c result within the past 6 months of enrollment will not be counted toward overall recruitment goals, and will be analyzed separately.

**Observation and Recording of Adverse Events:** Subjects will be required to report AEs. Open-ended questions and questions specific to SH and DKA will be included in all subject outreach contacts. In addition, the Global Post-market Surveillance data base (Tandem Diabetes Care, Inc.) will be queried monthly to determine the incidence of SH and/or DKA reported by study subjects (see **APPENDIX C** for surveillance procedures).

An AE form will be completed for every adverse event reported by a subject and verified by trained study personnel. Any medical management of an event and the resolution of the event must be recorded within the internal database utilized by Tandem's Global Post-

market Surveillance team (CRM), as the source documentation, and on the appropriate eCRF using medical terminology.

**Patient-reported Outcomes:** Questionnaires and surveys suitable for subjects being treated for type 1 diabetes (see **APPENDIX D**) will be electronically deployed to subjects at times specified in the Data Collection Timeline.

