Periodic Data Collection procedures	
100% of calls to Tandem Customer Technical Support will be screened for reportable AEs based on the definitions of SH and DKA included in this protocol. Outreach surveys will be deployed to all study participants: Monthly to collect AE incidence, and at 3, 6 and 12 months to collect other PROs (See Table 1).

Management of Adverse Events	
Safety information will be collected on an ongoing basis throughout the study as Tandem becomes aware of device-related AEs. These events will be recorded electronically from both inbound reports from customers and assessed through outreach to patients. The event, date of onset, severity, seriousness, duration and relationship to the device will be documented. All reported device-related AEs will be followed until they are adequately resolved or stabilized, until study completion/termination, or until number of outreach attempts made by clinical personnel corresponds with company's Customer Technical Support policy for adverse and device issue event outreach, whichever comes first. Safety events will be summarized based on FDA codes.

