### **Reportable Adverse Events:**

For this protocol, a reportable adverse event includes any untoward medical occurrence that meets one of the following criteria, as defined below:

1. Hypoglycemia meeting the definition of severe hypoglycemia (SH)
2. Diabetic ketoacidosis (DKA)
3. A serious adverse event (SAE)
4. An adverse device effect (ADE)

Hypoglycemia and hyperglycemia not meeting the criteria below will not be recorded as adverse events unless associated with an adverse device effect (ADE). Skin reactions from sensor placement are only reportable if severe and/or if they required treatment.

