#### **Serious Adverse Event (SAE):**

In accordance with 21 CFR Parts 803 and 812, a SAE is defined as any untoward medical occurrence that:

- Results in death,
- Is life-threatening,
- Requires hospitalization or prolongation of existing hospitalization,

- Results in persistent or significant disability/incapacity or substantial disruption of the ability to conduct normal life functions,
- Is a congenital anomaly or birth defect, or
- Is considered a significant medical event by the investigator based on medical judgement (e.g., may jeopardize the subject or may require medical/surgical intervention to prevent one of the outcomes listed above).

Medical and scientific judgement will be exercised in deciding whether medical events that may not be immediately life-threatening or result in death or hospitalization, but may jeopardize the subject or may require intervention to prevent one of the other outcomes listed in the definition above, should also be considered serious. A serious adverse event must be reported to the FDA as soon as possible, within a maximum of 15 calendar days.

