### **Unanticipated Adverse Device Effect (UADE)**

In accordance with 21 CFR Part 812, an UADE is any serious adverse effect on health or safety or any life-threatening problem or death caused by, or associated with, a device, if that effect, problem, or death was not previously identified in nature, severity, or degree of incidence in the risk assessment, the ICF as well as the protocol, or any other unanticipated serious problem associated with a device that relates to the rights, safety or welfare of subjects. An unanticipated device effect must be reported to the IRB within 5 business days and to the FDA within 10 business days.

In contrast to a UADE, an anticipated SAE is any SAE, the nature or severity of which has been reported in clinical trials of the Control-IQ System, or reported to Tandem Diabetes Care, Inc. by users of the t:slim X2 insulin pump. AEs reported during clinical studies of the Control-IQ system and post-market vigilance of the t:slim X2 insulin pump include, but are not limited to, the events shown below. The following device issues are anticipated and will not be reported on a Device Issue Form but will be reported as an Adverse Event if the criteria for AE reporting described above are met:

- Component disconnections
- CGM sensors lasting fewer than the number of days expected per CGM labeling
- CGM tape adherence issues
- Pump infusion set occlusion not leading to ketosis
- Battery lifespan deficiency due to inadequate charging or extensive wireless communication
- Intermittent device component disconnections/communication failures not leading to system replacement
- Device issues clearly addressed in the user guide manual that do not require additional troubleshooting
- Skin reactions from CGM sensor placement or pump infusion set placement that do not meet criteria for AE reporting

In addition, if the device issue is listed in Tandem Procedure QS-045, FDA Medical Device Reporting will be anticipated and not reported on a Device Issue Form. Any other device-related SAE will be considered an unanticipated adverse device event (UADE).

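### The support-call screen and the database query name only SH and DKA, although SAEs and ADEs are also reportable; the gap falls mainly on SAEs not related to the device

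*Combined protocol and SAP*

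**What the plan says.** Two sentences set out what is looked for in participants' own contacts with the sponsor. In the Synopsis, under Periodic Data Collection procedures, all Customer Technical Support calls "will be screened for reportable AEs based on the definitions of SH and DKA included in this protocol". In Measurements and Evaluations, under Observation and Recording of Adverse Events, the post-market surveillance database "will be queried monthly to determine the incidence of SH and/or DKA reported by study subjects", with a pointer to Appendix C for the procedure.

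The set of events the study wants is wider. Reportable Adverse Events lists four categories: SH, DKA, any SAE and any ADE. Adverse Event Definitions says that all AEs in all subjects will be documented, whatever their relation to the device. The SAE section requires SAEs to go to the FDA "within a maximum of 15 calendar days" and does not limit this to device-related events. The UADE section says that unanticipated device effects "must be reported to the IRB within 5 business days and to the FDA within 10 business days".

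Other routes are described. The Synopsis, under Management of Adverse Events, collects device-related AEs continuously as the sponsor learns of them, from inbound reports and from outreach. All outreach contacts carry open-ended questions as well as questions on SH and DKA, and AE outreach is monthly. Subjects are told to report AEs spontaneously. Adverse Event Definitions and Responsibilities of the Principal Investigators both name incoming support calls as a source of AE information.

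**The concern.** Safety is the study's main purpose, there are no clinic visits, and the support line is an obvious place for a participant to mention a medical event. The written screen tells staff to look for two of the four kinds of event that the study counts as reportable. The screening sentence also mixes two scopes: it uses the plan's term for the four-category set and then supplies only two of the definitions.

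If staff apply the sentence as written, a participant who mentions a hospital admission for something other than SH or DKA matches neither the call screen nor the database query. What is at stake is the completeness of the SAE record and of the FDA reporting that follows from it. The SH and DKA incidence rates are not at stake, because both rules name those events.

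**Working it through.** No figure in the plan bears on this point, so the check is to set the stated routes against each reportable category. SAEs that are themselves SH or DKA are counted in the first row.

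| Reportable event | Call screen names it | Database query names it | Ongoing inbound collection | Other stated routes |
|---|---|---|---|---|
| SH, DKA | Yes | Yes | If device-related | Specific and open-ended outreach questions; spontaneous report |
| ADE | No | No | Yes | Open-ended outreach question; spontaneous report |
| Other SAE, device-related | No | No | Yes | Open-ended outreach question; spontaneous report |
| Other SAE, not device-related | No | No | No | Open-ended outreach question; spontaneous report |

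Step 1, scope. Both inbound rules name SH and DKA, and Reportable Adverse Events lists four categories. Coverage by name is 2 of 4. This counts categories, not events, and says nothing about what share of events would be missed.

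Step 2, what the other routes recover. The ongoing collection in the Synopsis covers device-related AEs from inbound reports. An ADE is by definition an event that the device may have caused or contributed to, so ADEs and device-related SAEs have a stated inbound route despite the narrow screen.

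Step 3, what is left. The last row has no inbound rule that names it. Such an event can still reach the study in three ways: the participant repeats it in answer to a monthly open-ended question; the participant reports it to the study team directly; or support staff act on the general statements that incoming calls are an AE source, although their written screen does not name it.

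Step 4, order of decisions. Relationship to Study Device leaves causality to the clinical investigator, and Adverse Event Definitions places that review after the AE form has been verified. A route that depends on device-relatedness therefore needs a provisional judgement before the investigator has seen the event. A screen on all four categories would not need that judgement.

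Step 5, size. The documents give no expected rate of SAEs unrelated to the device and no share of events first mentioned on support calls. The number at risk cannot be calculated, and I give none.

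**The case against.** The strongest reply is that the two sentences are not the whole system. Device-related AEs are collected on awareness. The investigator must report AEs in a timely manner using incoming calls, with no restriction to SH and DKA. Data Management sends unscheduled participant contacts and device issues to the eCRF. The schedule row for incoming AEs is not restricted to the two endpoints. The query itself is an added step, since its sentence opens "In addition, the Global Post-market Surveillance data base (Tandem Diabetes Care, Inc.) will be queried monthly" and its stated purpose is incidence. Appendix C and the sponsor's outreach and device-reporting procedures, where triage and escalation would be expected, are not in the available text. Most of this stands, and it confines the point to SAEs unrelated to the device. It does not remove the point: a general duty to use incoming calls does not tell call staff what to recognize, and the only written criteria are the two definitions.

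A reader might go further and infer that, because a month is longer than each reporting limit, the limits cannot be met, IRB notices will be late, and SAE and ADE counts will be too low. The documents do not support that. Nothing routes expedited reports through the monthly query; support calls are screened in their own right and device-related events are collected continuously. The 5- and 10-business-day limits apply to unanticipated device effects only, the 15-calendar-day limit applies to SAEs, and no day limit is stated for ADEs in general. No section says when a clock starts, so a breach cannot be shown. Any share of late reports would have to assume that the query is the only route, which the text contradicts. Institutional approval of the protocol also makes the investigator responsible for keeping the IRB informed of SAEs and UADEs.

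**Conclusion.** The point holds as a mismatch of scope. The call screen and the database query each name two of the four reportable categories, and the plan separately promises that all AEs will be documented. The practical effect is mainly on SAEs not related to the device, which may be under-captured when a support call is the only place a participant mentions them. The size cannot be stated from the documents.

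The conclusion assumes that staff apply the screening sentence as written and that Appendix C does not already widen it. If Appendix C does, what remains is an inconsistency of wording to correct in the body of the protocol. The missing clock start is a separate point of clarity and does not show that reports would be late.

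**What to change.** In the Synopsis (Periodic Data Collection procedures) and in Observation and Recording of Adverse Events, apply the call screen and the database query to all four categories in Reportable Adverse Events, matched to study participants. Keep the monthly SH/DKA query for tabulating incidence. If Appendix C already does this, bring the two sentences into line with it and cite it.

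As a clarification only, state in the SAE and UADE sections when each clock starts, and that inbound calls, not the monthly query, trigger it.

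The cost is protocol wording, a change to the screening filter and more records for existing staff to review. Matching to participants looks feasible, because Enrollment procedure already produces daily contact lists from the sponsor's customer systems.
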